6.3 Study Duration

Total study duration is expected to be approximately 36 months. Patient enrollment is expected to occur over a 24-month period, with follow-up continuing until assessments of the primary and critical secondary objectives are completed for all treated patients. Please consult Section 7.6.2 regarding recommended procedures and follow-up after treatment discontinuation.

6.4 Study Completion, Survival Extension Period, End-of-Trial

The study is considered complete when sufficient information is available to enable assessment of the primary endpoint and selected secondary endpoints, including MRD eradication in the months following initiation of investigational therapy. In the weeks subsequent to a determination that sufficient information is available for these assessments, a date for database lock will be assigned, and any outstanding inquiries concerning data elements will be resolved. The **Study Completion** date will be the date beyond which study data is no longer entered into the primary database (this study completion date generally precedes the date on which the database lock occurs by several weeks/months).

In the event that patients continue to remain alive and/or alive without evidence of AML recurrence/progression, a **Survival Extension Period** may be implemented, in which patients who are alive (with and without evidence of AML recurrence) will continue to be followed at regular intervals for evidence of disease progression and overall survival status. During this **Survival Extension Period**, Investigators are encouraged to continue evaluation of patients at a schedule appropriate for patients with AML in remission or recurrent AML. Data collection by the Sponsor during this **Survival Extension Period** will be limited to information pertaining to AML disease recurrence (for patients without evidence of disease recurrence at time of database lock) and survival status for all patients alive at time of database lock. Information concerning AEs considered at least possibly related to SL-401 that were unresolved at time of database lock will also be collected. This disease recurrence, survival and unresolved AE data will comprise a **Supplemental Database**. The **End-of-Trial** occurs following the death of the last patient remaining alive during the **Survival Extension Period** follow-up, or at a time when the Investigators/Sponsor conclude that ongoing survival follow-up is no longer advisable/feasible. In situations where all patients have experienced AML recurrence and/or are deceased at time of **Study Completion**/initial database lock, then the **Survival Extension Period/Supplemental Database** will not be considered necessary, and the **End-of-Trial** will occur at the same time as **Study Completion**.

7 Study Treatment Identification, Administration, and Schedule

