9.7 Survival Monitoring: Approximately Every 90 Days after End of Treatment

- Survival status and response/disease progression status (for patients in PR/CR at End of Treatment), continuing until assessments of the primary and secondary objectives are completed for all patients; survival status may be performed by telephone contact.
- Patients who undergo SCT will be followed for the occurrence of VOD as part of survival monitoring.
- A blood sample for immunogenicity studies will be collected at least 16 weeks to up to 20 weeks after the last SL-401 dose.

Table 5: Study Events Schedule for Cycle 1 (Study Day -14 to Study Day 28-35)

Tests and Observations	Study Day -14 to -4	Cycle 1					
		Study Day -1 to 0	Study Days 1-5 (Up to Study Day 10 if Infusion(s) Held)		Study Day 8±3 ⁽ⁿ⁾ , 15±3, and 21±3	Study Day 28±3 ^(o)	Study Day 35±3, Then Every 7±3 days
			SL-401 Treatment				Delayed End of Cycle for Toxicity Resolution Only if Required
Screening	Pre-treatment	Pre-Infusion	Infusion	End of Cycle ^(o)			
Informed consent form	X						
Inclusion/exclusion criteria	X						
Medical history including prior therapy, concomitant medications	X						
Concomitant Medications		X			X	X	X
ECOG performance status	X					X	X
Physical examination	X	X				X	
Pregnancy test ^(a)	X						
Vital signs and weight ^(b)	X	X	X	X		X	X
12-lead ECG ^(c)	X	X	X	X (Infusions 1, 5)		X	X
ECHO or MUGA scan ^(d)	X						
Hematology ^(e)	X	X	X		X	X	X
Serum electrolytes ^(f)	X	X	X		X	X	X
Serum albumin ^(g)	X	X	X		X	X	X
Serum chemistry ^(h)	X	X	X		X	X	X
Coagulation parameters: PT/INR, aPTT	X		X		X	X	X
Urinalysis ⁽ⁱ⁾	X		X (Infusion 1)		X	X	X
Tumor response assessment: Bone marrow aspiration + biopsy ^(j)	X						
Administration of premeds ^(k)			X				
SL-401 administration ^(l)				X			
Pharmacokinetic sampling ^(m)			X (Infusions 1, 5)	X (Infusions 1, 5)			
Immunogenicity sampling			X (Infusion 1)		X (day 15)	X	
Vision assessment	X				X (day 21)		
AE and SAE monitoring			X	X	X	X	X

a Urine or serum pregnancy test must be performed within 1 week prior to treatment in women of childbearing potential.

b Vital signs should be performed after patient is sitting for 3-5 minutes. If during dosing period, vital signs should be taken immediately prior to infusion, immediately after completion of infusion, and 30, 60, and 240 minutes post-infusion.

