- l After the follow-up visit, patients will then be followed every 90 days for survival status for at least one year following the start of SL-401. The survival follow-up may be by telephone contact. Patients who undergo SCT will be followed for the occurrence of VOD as part of long-term follow-up. A blood sample for immunogenicity studies will be collected at least 16 weeks to up to 20 weeks after the last SL-401 dose.
- m For patients who live a considerable distance from the Study Center, for whom weekly travel to the Study Center is not feasible, the Day 8, 15, and 21 (\pm 3 days) laboratory assessments (blood and urine) may be submitted to a local laboratory, although the results must be evaluated by the Study team. Concomitant medication and AE monitoring on these days will take place via telephone contact. In situations where SL-401 is not administered over 5 consecutive days (i.e., treatment delays because of AEs or other factors) and an infusion is to be administered on Day 8, all pre-infusion/infusion evaluations should be conducted, in addition to concomitant medications recorded. Upon completion of the 5th Cycle 1 infusion (Day 8, 9 or 10), the blood/urine/concomitant medication and AE assessments should be planned for Day 15, as indicated in the table.
- n The end-of-the cycle evaluations (Day 28 or thereafter) may also serve as the pre-infusion evaluations for the subsequent cycles; these do not need to be duplicated on successive days unless there is an abnormality or other clinically relevant reason for repeat evaluation.

Table 7: Time Points for Pharmacokinetic Blood Draws and ECGs

Collection Timepoint	Day			
	Cycles 1 and 3: Day 1/Infusion 1		Cycles 1 and 3: Day 5/Infusion 5	
	ECG	PK	ECG	PK
Pre-Infusion	X	X	X	X
Immediately After End of Infusion (time recorded)		X		X
15 Minutes Post-Infusion		X		X
30 Minutes Post-Infusion	X	X	X	X
45 Minutes Post-Infusion		X		X
60 Minutes Post-Infusion	X	X	X	X
90 Minutes Post-Infusion		X		X
120 Minutes Post-Infusion		X		X
180 Minutes Post-Infusion		X		X
240 Minutes Post-Infusion		X		X

10 Adverse Events and Safety Evaluation

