11.5.2 Relapse (progression) – free Survival (RFS/PFS)

Relapse-free survival is defined as the proportion of patients who remain free of AML recurrence (hematologic) and alive. According to current WHO classification, a myeloblast population comprising greater than 5% of nucleated cells in the bone marrow or blood is required for diagnosis of AML relapse following CR/CRi (if no peripheral blasts are present, then a confirmation aspirate is required ≥ 1 week subsequent to the aspirate at which $>5\%$ blasts were identified). RFS will be evaluated via Kaplan-Meier analysis (in which patients who are lost to follow-up or who are not evaluable for recurrence have data censored), and via direct proportional analysis (percentage of patients receiving treatment [or treatment at MTD or otherwise derived Stage 2 dose] who are alive and without evidence of AML recurrence). Median, 6- and 12-month RFS rates will be evaluated.

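### Four non-matching end-of-follow-up rules, and an undefined SAP cut-off, permit the database to close before late (chiefly Stage 2) patients reach Month 12

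*Protocol*

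**What the plan says.** Four places in the protocol say when follow-up ends.

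- **Section 6.4** defines study completion: "The study is considered complete when sufficient information is available to enable assessment of the primary endpoint and selected secondary endpoints". The only secondary endpoint it names is MRD eradication in the months after treatment starts. The completion date is the point after which nothing more enters the primary database. Later recurrence and survival data go to a Supplemental Database, collected in an extension period that is optional.
- **Section 6.3** describes "follow-up continuing until assessments of the primary and critical secondary objectives are completed for all treated patients". It also gives the timeline: "Total study duration is expected to be approximately 36 months" and "Patient enrollment is expected to occur over a 24-month period".
- **Section 9.7** has survival and disease-status monitoring "continuing until assessments of the primary and secondary objectives are completed for all patients", with no qualifier on the secondary objectives.
- **Table 6 footnote l** states that "patients will then be followed every 90 days for survival status for at least one year following the start of SL-401". This concerns survival status, and a telephone call is enough.

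RFS and OS are secondary objectives (Protocol 4.2). Protocol 11.5.2 promises: "Median, 6- and 12-month RFS rates will be evaluated"; SAP 4.3.2 repeats the 6- and 12-month rates. Both documents also plan a direct proportion alive and free of recurrence.

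SAP 4.3.2 and 4.3.3 refer to an analysis cut-off date. SAP 3.12, on timing of analysis, gives neither a date nor a trigger for it, and the SAP does not mention the Supplemental Database.

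**The concern.** The four statements do not ask for the same thing. Section 6.3 limits the secondary objectives to those that are *critical* and 6.4 to those that are *selected*; neither word is defined. Section 9.7 has no such limit. Table 6 footnote l sets a one-year minimum, but not for relapse data.

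Section 6.4 matters most because it alone fixes when data stop entering the primary database, and it is the least demanding of the four. Taken at its word, it is met once MRD conversion can be assessed, which may be well before the last patients reach Month 12. The study is open label (Protocol 11.7) and no cut-off is fixed in advance, so the date could be set with outcomes in view.

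The patients exposed are those who enrol last. Those are chiefly Stage 2, the MRD-positive group that SAP 3.5 singles out for efficacy analysis.

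**Working it through.** **The plan's own figure.** 36 months in total less 24 months of enrolment = 12 months for the last patient. That just covers a 12-month RFS estimate, so on the stated timeline the loss is 0%.

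**Inputs from the documents.** Enrolment 24 months (Protocol 6.3). Enrolled at database lock: 18 in Stage 1 and 9 in Stage 2 (SAP 3.1). Up to six 28-day cycles, dosed on Days 1 to 5 (Protocol 7.5.2). First post-baseline marrow about 28 days after the start of Cycle 2 (Protocol 6.2.3).

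**Assumptions.**
- Accrual is uniform.
- Stage 2 follows Stage 1 and fills the last 24 × 9/27 = 8 months.
- Time to relapse or death is exponential with 12-month RFS of 40% (range 30% to 50%), so λ = −ln(0.4)/12 = 0.0764 per month.
- Lock comes F months after the last first infusion. F = 6 is close to the end of six cycles (168 days, 5.5 months). F = 2 is close to the last patient's Cycle 2 marrow (56 days, 1.8 months). No document gives these values of F.
- Relapse-free patients are censored administratively at lock. The SAP does not do this; see the last step.

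**Formulas.**
- Share short of 12 months, for accrual over A months: (12 − F)/A, at most 1. With F = 6: 6/24 = 25% of all patients; 6/8 = 75% of Stage 2.
- Expected at risk at Month 12 in Stage 2: 9 × 0.40 × (1 − share). With F = 6: 9 × 0.40 × 0.25 = 0.9.
- Direct proportion alive and relapse-free in Stage 2 at lock: [exp(−λF) − exp(−λ(F + 8))]/(8λ). With F = 6: (0.632 − 0.343)/0.611 = 0.47.
- Standard error (SE) of 12-month RFS: large-sample Greenwood form. With F = 12 and n = 27 it reduces to √(0.4 × 0.6/27) = 0.094.

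| F (months) | All patients short of 12 months | Stage 2 short of 12 months | Stage 2 at risk at Month 12 (of 9) | SE, all 27 | SE, Stage 2 | Direct proportion, Stage 2 |
|---|---|---|---|---|---|---|
| 12 | 0% | 0% | 3.6 | 0.094 | 0.163 | 0.30 |
| 6 | 25% | 75% | 0.9 | 0.099 | 0.205 | 0.47 |
| 2 | 42% | 100% | 0 | 0.108 | not estimable | 0.64 |

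With 12-month RFS from 30% to 50%, the Stage 2 number at risk is 2.7 to 4.5 for F = 12 and 0.7 to 1.1 for F = 6.

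The direct proportion has no time horizon, so it rises as the lock moves earlier. With a true 12-month RFS of 0.40, it would read 0.47 or 0.64 for locks at 6 or 2 months.

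**The SAP censoring rule.** SAP 4.3.2 censors living, relapse-free patients at their last treatment before the cut-off. The last planned dose of Cycle 6 is Day 5 × 28 + 5 = 145, about 4.8 months. Without long delays or extra cycles, no such patient counts as followed to Month 12, whatever the lock date. Beyond that point the risk set holds only patients who later relapse or die, apart from any censored for starting another anticancer therapy. The 12-month Kaplan-Meier estimate is then unreliable even with full follow-up.

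**The case against.** The strongest reply is that the four statements serve different purposes: 6.3 describes duration, 9.7 governs survival monitoring, footnote l is a per-patient minimum, and 6.4 concerns the database. Read together, with marrow assessments to Month 12 and 24 months of enrolment within 36, they deliver 12 months for everyone. It is true that this is the plan, and that early closure needs 6.4 to be read alone. But 6.4 is the section that stops data entry. The 36 months is an approximate expectation and not a lock condition, and the one-year minimum does not secure relapse data.

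A reader might infer that an unblinded sponsor will judge when information is sufficient. The documents do not say so. Section 6.4 names nobody for that decision; it mentions investigators and sponsor only for the later end of trial. Unblinded here means no more than open label. The gap is that no decision-maker is named.

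A reader might also infer that 12-month RFS will lose much of its follow-up. That does not hold for the whole cohort: even with early closure, the SE for all 27 patients moves only from 0.094 to between 0.099 and 0.108. It can hold for Stage 2, and only if the lock is early.

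It is also fair to say that RFS and OS are estimated descriptively, with no decision rule attached. The only success rule is MRD conversion in at least 2 of 15 patients. That limits the stakes but does not remove the contradiction.

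**Conclusion.** The concern holds as a conflict between stated rules together with a missing definition. It does not show that early closure is intended. Sections 6.3, 6.4, 9.7 and Table 6 footnote l do not match, the operative rule in 6.4 permits a lock before late patients reach Month 12, and the SAP cut-off is undefined.

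On the stated timeline the cost is nil. If the lock came 6 months after the last first infusion, the loss would be modest overall but serious for Stage 2, and the direct relapse-free proportion would be inflated. The Stage 2 figures depend on the assumed 8-month accrual block, uniform accrual, 40% 12-month RFS and administrative censoring.

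The lock rule alone does not rescue 12-month RFS, because censoring at last treatment undermines the Kaplan-Meier estimate independently.

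**What to change.** 1. Use one rule in Protocol 6.3, 6.4, 9.7 and Table 6 footnote l, and in SAP 3.12. The analysis cut-off is no earlier than 12 months after the last treated patient's first infusion, so that every treated patient has reached 12 months or has died, withdrawn or been lost before then. Later data go to the Supplemental Database.
2. In 6.4, replace the undefined qualifiers with a list of endpoints that must be assessable, including RFS and OS, and say who declares the study complete.
3. In SAP 4.3.2, censor relapse-free patients at the last disease assessment before the cut-off instead of at last treatment.
4. SAP 3.1 already reports enrolment at database lock. If the lock has happened, state the actual cut-off, its basis and the distribution of follow-up in the study report.

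The cost is mainly wording. The rule fits the protocol's own 24 + 12 = 36 months. The sponsor gives up an early lock. The 1-month window on follow-up marrows and the confirmatory aspirate at least a week later may add a few weeks to the 36 months.

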7.1 Product Manufacturing and Characterization

Refer to the IB for full details of product manufacturing and characterization.

7.2 Recommended Medications per Institutional Guidelines/Practices

It is recommended that patients receive the following types of prophylactic therapies/regimens per institutional guidelines/practices:

- Antibacterial: ciprofloxacin, levofloxacin, or an equivalent antibiotic
- Antifungal: fluconazole, voriconazole, or an equivalent antifungal
- Antiviral: acyclovir, valacyclovir or an equivalent antiviral

7.3 Allowed Medications/Therapies

All patients may receive supportive care measures as clinically indicated, including prophylactic antibiotics, antihistamines, antiemetics, albumin, fluids (hydration), and supportive measures. Patients may receive growth factor support and/or blood product transfusions as per the discretion of their physician.

Albumin 25 g IV daily should be administered if serum albumin is between 3.0-3.5 g/dL (30-35 g/L) on days that dosing occurs or if it is <3.0 g/dL (30 g/L) on days when treatment has been withheld or in the immediate post-treatment period. The Investigator has discretion with regard to frequency of administration per product and institutional guidelines.

7.4 Prohibited Medications/Therapies

Prior to discontinuation of SL-401, patients may not receive investigational or non-investigational anticancer or anti-leukemia agents, including cytotoxic chemotherapy agents, hypomethylating agents (5-azacytidine, decitabine, and others), or anticancer tyrosine kinase inhibitors (including imatinib, ruxolitinib, sorafenib, and others) or therapeutic monoclonal antibodies.

7.5 SL-401

7.5.1 SL-401 Description and Storage

SL-401 is a novel biologic fusion protein comprised of recombinant human IL-3 genetically fused to truncated diphtheria toxin protein. SL-401 targets the IL-3R, which is over-expressed on the CSCs and bulk of various leukemias and hematopoietic malignancies relative to normal hematopoietic stem cells and other hematopoietic cells.

SL-401 drug product is prepared in two formulations and dosage forms.

- SL-401 Injection is a non-preserved, sterile, liquid dosage form supplied in sterile 2 mL glass vials containing 1 mL of sterile SL-401 solution (1 mg/vial) and should be stored frozen at -20°C ($\pm 5^\circ\text{C}$).
- SL-401 for Injection is a non-preserved, sterile, powder for solution supplied in sterile 3 mL glass vials and should be stored at -20°C ($\pm 5^\circ\text{C}$).

Documentation stating the product's expiry date will be provided with each shipment.

7.5.2 Dose, Schedule, and Duration of Treatment

Patients will receive SL-401 by IV infusion over 15 minutes for 5 consecutive days (or 5 doses over a period not to exceed 10 days if postponement is required for toxicity) of a 28-day cycle in the absence of disease progression or other withdrawal criteria.

Refer to the Pharmacy Manual for details regarding SL-401 administration.

Patients with evidence of ongoing disease control during treatment (without evidence of clinically significant progressive disease or intolerable toxicity) may receive repeated cycles of

SL-401 even if eradication of MRD, in the judgment of the Investigator, is not attained. Patients can receive up to 6 total cycles of SL-401 as long as there is ongoing evidence of AML remission, as determined by the Investigator. The administration of additional cycles of SL-401 (> 6 cycles) must be discussed with the Medical Monitor at which time the individual patient's potential risk/benefit of further treatment will be assessed.

7.5.3 SL-401 Premedication and Dose Preparation and Administration

7.5.3.1 Premedication

Patients will receive the following premedication approximately 60 minutes before each SL-401 infusion:

- Acetaminophen 650 mg by mouth (PO)
- Diphenhydramine 50 mg IV
- Methylprednisolone 50 mg IV (or an equivalent dose of another corticosteroid)
- Ranitidine 50 mg IV (or an equivalent dosage of another H₂-histamine antagonist)

7.5.3.2 SL-401 Dosage Preparation

SL-401 is administered as a 15-minute IV infusion. SL-401 is prepared for administration by the pharmacy. The total per-patient dose is calculated based on patient body weight in kilograms (kg) including one decimal place, and the patient's dosing cohort, as described in Section 6.2 ($\mu\text{g}/\text{kg}$ dose \times patient weight in kg, including one decimal place [example: 7 $\mu\text{g}/\text{kg} \times 70.3\text{kg}$]). Additional dose preparation supplies and instructions are provided in detail within the Pharmacy Manual.

7.5.3.3 Inpatient and Outpatient Setting for Dose Administration

In Stage 1, the first cycle of SL-401 must be administered in the inpatient setting, with hospitalization beginning the day of the first infusion of SL-401 (or a prior day) and ending approximately 24 hours after the last infusion of SL-401. Subsequent cycles of SL-401 can be administered in the inpatient setting or in a suitable outpatient ambulatory care setting that is equipped for intensive monitoring of patients with hematopoietic malignancies undergoing treatment, per the discretion of the Investigator and institutional guidelines and capabilities. Patients will be monitored for at least 4 hours following the administration of each SL-401 infusion.

7.5.4 Patient Monitoring Procedures During the SL-401 Dosing Period

During each cycle, tests and procedures that may result in withholding of a scheduled SL-401 infusion, largely based on unresolved manifestations of fluid retention and/or other relevant acute toxicities during daily dosing, are described below and summarized in [Table 5](#) and [Table 6](#).

Vital Signs: Blood pressure, heart rate, respiration rate, body temperature, and pulse oximetry during dosing period (usually Days 1, 2, 3, 4 and 5): immediately prior to infusion, immediately

after completion of infusion, and 30, 60, and 240 minutes post-infusion; and Days 8, 15, 21 and 28.

Diagnostic Tests:

- During dosing period prior to SL-401 infusion (usually Days 1, 2, 3, 4, 5) and Days 8, 15, 21 and 28: Complete blood count (CBC) with differential, platelets, sodium, potassium, chloride, bicarbonate, blood urea nitrogen (BUN), creatinine, glucose, total protein, albumin, calcium, phosphorus, uric acid, total bilirubin, ALT, AST, alkaline phosphatase, lactate dehydrogenase (LDH), prothrombin time (PT) or International Normalized Ratio (INR), and activated partial thromboplastin time (aPTT)
- Days 1 (prior to SL-401 infusion), 8, 15, 21, and 28: routine urinalysis
- For temperature $\geq 38^{\circ}\text{C}$, draw blood culture $\times 2$, and collect urine for urinalysis and culture

7.5.5 Dose Delays/Modifications and Management Procedures for Toxicities Associated with SL-401

During the dosing period for each cycle, individual SL-401 infusions may be delayed to allow for toxicity resolution.

If dosing is resumed within a cycle, any subsequent doses in that cycle must be administered within the first 10 days of that cycle; thus, patients may receive fewer than 5 doses during a given study cycle. SL-401 may be resumed at the same dose or a reduced dose for Grade 3/4 toxicities (see [Table 3](#) and Section [7.5.5.11](#)).

